13.5 Secondary Objectives, Endpoints, Analysis Plans

The secondary objectives include to determine whether Avmacol® increases the mercapturic acids of acrolein and crotonaldehyde and the mercapture acids of tobacco carcinogens normalized by bio-measurement of tobacco exposure and upregulates the NRF2 target gene transcripts in the buccal cells of current smokers and to evaluate for a dose-response relationship between Avmacol® and the detoxification of tobacco carcinogens and the expression of NRF2 target gene transcripts and the relationship between systemic study agent exposure and biomarker modulation. The secondary endpoints are the changes in mercapturic acids of acrolein and crotonaldehyde levels (from baseline to end-of-intervention for each Intervention Period), the changes in mercapturic acids of tobacco carcinogens, normalized by bio-measurement DCP Protocol Template Version 8.5 08/31/2016

of tobacco exposure (from baseline to end-of-intervention for each Intervention Period) and in NRF2 target gene transcripts (from baseline to day 4-8 and to end-of-intervention for each Intervention Period) assessed by the expression of *NQO1* after Avmacol® intervention. Similar to the primary endpoint, each of the changes following 4 tablets of Avmacol® per day and after 8 tablets of Avmacol® per day will be evaluated separately. For changes in tobacco carcinogens, two-sided paired t tests will be performed to evaluate the significance of changes. For changes in NRF2 target gene transcripts, linear mixed effects models will be fitted to evaluate the significance of changes since each participant will have two changes in each Intervention Period (from baseline to day 4-8 and to end-of-intervention). Linear mixed effects models will be also fitted to determine whether there is a dose-response relationship between the Avmacol® dose and the change in carcinogen metabolites and the change in the NRF2 target gene transcripts since each participant will have more than one change for each endpoint. Spearman correlation coefficient will be calculated to evaluate the correlation between systemic study agent exposure and biomarker modulation.

In addition, we will also explore whether the *GSTM1* and *GSTT1* genotypes are important genetic modulators of detoxification of tobacco carcinogens. This will be evaluated by comparing the change in benzene for each dose level between *GSTM1*-null and *GSTM1*-positive subjects and between *GSTT1*-null and *GSTT1*-positive subjects, respectively, using two-sided two-sample t tests. For all of the secondary and exploratory analyses, adjustment for multiple comparisons will not be performed. However, the number of comparisons will be reported and we will also cautiously interpret the findings. For both primary and secondary endpoints, two-sample t tests will be performed to evaluate whether there is a significant sequence effect (e.g. receiving 4 tablets per day in the first Intervention Period vs. receiving 4 tablets per day in the second Intervention Period). Regression techniques will be used to control for baseline levels and potential confounders if necessary. Also, if the normality assumption is violated, potential transformation will be sought or nonparametric methods such as signed rank test will be performed. For any of the endpoints, if a missing rate of >15% is observed, multiple imputation by chained equations will be performed.

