8.2 Secondary Endpoints

The secondary endpoints are:

- To determine the changes (from baseline to end-of-intervention for each Intervention Period) in the urinary excretion of the mercapturic acids of acrolein and crotonaldehyde after Avmacol® intervention. Similarly, the urinary biomarkers will be normalized by the urinary creatinine levels. The changes following 4 tablets of Avmacol® per day and after 8 tablets of Avmacol® per day will be calculated separately for each tobacco carcinogen.
- To determine whether Avmacol® increases the urinary excretion of the mercapturic acids of tobacco carcinogens, normalized by bio-measurement of tobacco exposure. Bio-measurement of tobacco exposure will be assessed by the total urinary levels of nicotine and major nicotine metabolites (i.e., the sum of the molar concentrations of nicotine and major nicotine metabolites in urine). The changes following 4 tablets of Avmacol® per day and after 8 tablets of Avmacol® per day will be calculated separately for each tobacco carcinogen.
- To determine the changes (from baseline to day 4-8 and to end-of-intervention) in the NRF2 target gene transcripts, assessed by the expression of *NQO1*, in the buccal cells after Avmacol® intervention. The changes following 4 tablets of Avmacol® per day and after 8 tablets of Avmacol® per day will be determined separately.
- To determine whether there is a dose-response relationship between the Avmacol® dose and the detoxification of tobacco carcinogens and the change in the NRF2 target gene transcripts.
- To determine the relationship between systemic study agent exposure, assessed by the total urinary levels of sulforaphane and its glutathione-derived metabolites (i.e., the sum of the molar concentrations of sulforaphane and its glutathione-derived metabolites in urine), and changes in detoxification of tobacco carcinogens and NRF2 target gene transcripts.

The study also includes the following explorative endpoints:

- To determine whether the *GSTM1* and *GSTT1* genotypes are important genetic modulators of detoxification of tobacco carcinogens. The change in the urinary excretion of the mercaptoruinc acids of tobacco carcinogens will be compared between *GSTM1*-null and *GSTM1*-positive subjects and between *GSTT1*-null and *GSTT1*-positive subjects.
- To bank specimens for future research including tobacco gene signature in nasal brushing, and fixed buccal cells for nuclear morphometry.

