13. STATISTICAL CONSIDERATIONS

13.1 Study Design/Description

This is an open-label, randomized cross-over study to determine whether two different doses of Avmacol® (4 tablets per day for 10-14 days; 8 tablets per day for 10-14 days) increase the detoxification of tobacco carcinogens in otherwise healthy, current smokers. Participants will serve as their own controls based on a 2 x 2 cross-over design. Specifically, each participant will have two Intervention Periods (one period taking 4 tablets per day; the other taking 8 tablets per day) with a 10-14 day washout period in between to eliminate the potential carry-over effect.

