13.3 Accrual and Feasibility

We plan to accrue 61 eligible participants to initiate agent intervention. With an anticipated attrition rate of 33% or less (with respect to completing the intervention and having complete endpoint data), we expect to have at least 41 participants with evaluable endpoint data. Projected accrual is 2 participants per month.

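### The genotype question is tested only dose by dose, with no overall test per gene, although each completer contributes two changes

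*Combined protocol and SAP*

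**What the plan says.** Section 1.3 asks whether the GSTM1 and GSTT1 genotypes modulate detoxification under Avmacol treatment and names no dose. Section 8.2 repeats this without a dose split: "The change in the urinary excretion of the mercaptoruinc acids of tobacco carcinogens will be compared between" null and positive subjects for each gene. The items in 8.2 on change in urinary carcinogens and in NRF2 transcripts do say that the two doses are handled separately.

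Section 13.5 turns the genotype question into "comparing the change in benzene for each dose level between" the genotype groups, "using two-sided two-sample t tests". For secondary and exploratory analyses, "adjustment for multiple comparisons will not be performed"; the plan says it will report how many comparisons were made and interpret them cautiously.

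Section 13.1 states that "each participant will have two Intervention Periods", one at each dose. For dose-response, section 13.5 fits linear mixed effects models "since each participant will have more than one change for each endpoint". It does not extend that reasoning to genotype.

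**The concern.** Genotype is a fixed characteristic of the participant, so its effect is a between-person contrast, and both changes carry information on it. Each planned test uses only one of them. The plan then has two answers per gene, no overall answer to a question that names no dose, and no rule for reading a result that is significant at one dose and not at the other. Such a split result invites a dose-specific interpretation even when the underlying effect is the same at both doses.

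The answer has some weight. Section 2.3 sets a study of a related compound in smokers, where the effect was much stronger in participants null for both genes, against a 300-patient study where the effect did not depend on genotype. It uses the latter to suggest that the approach applies broadly.

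**Working it through.** **Inputs from the documents.** Section 13.3: "we expect to have at least 41 participants with evaluable endpoint data". Section 13.4: 0.50 SD, two-sided 2.5% per test, at least 80% power. Section 13.5: two-sided two-sample t tests without adjustment, taken here as 5% each.

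**Assumptions, not in the documents.** Genotype splits of 20/21 and 8/33; correlation r between a participant's two changes; equal SDs at the two doses unless stated.

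**The plan's own figures.** 61 × 0.67 = 40.9, so 41 is reproduced. The exact noncentral-t power of a paired test at n = 41, 0.50 SD and two-sided 2.5% is 80.5%, so the stated power is also reproduced. The plan gives no power or detectable difference for genotype.

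**Detectable genotype difference** (80% power, two-sided 5%, df 39). The mean of two equally variable changes has SD multiplied by √((1 + r)/2). Sample size, df and split are the same for both tests, so the proportional cut is 1 − √((1 + r)/2), whatever the split.

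| r | Cut | 20/21 split: 0.90 SD at one dose becomes | 8/33 split: 1.13 SD becomes |
|---|---|---|---|
| 0 | 29.3% | 0.63 | 0.80 |
| 0.25 | 20.9% | 0.71 | 0.90 |
| 0.5 | 13.4% | 0.78 | 0.98 |
| 0.8 | 5.1% | 0.85 | 1.07 |

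**Discordant results.** With a 20/21 split and a true 0.70 SD difference at both doses, one dose test has 58.9% power. At r = 0 the two tests are independent, so the chance that exactly one is significant is 2 × 0.589 × 0.411 = 48%. Simulation gives 41% at r = 0.25 and 33% at r = 0.5.

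**Overall test against the planned pair**, same setting:

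| r | At least one of two dose tests at 5% | Test of the mean change at 5% | Chance of at least one false positive from the pair, no genotype effect |
|---|---|---|---|
| 0 | 83% | 87% | 10% |
| 0.25 | 80% | 79% | 10% |
| 0.5 | 75% | 71% | 9% |
| 0.8 | 69% | 63% | 8% |

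At r = 0 the pair's entries are 1 − 0.411² = 83% and 1 − 0.95² = 9.75%; the others are simulated. If each dose test were held to 2.5%, the pair would find the effect in 64% of trials at r = 0.5, below the 71% for the mean.

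**Unequal genotype effects.** If the low-dose effect is a fraction f of the high-dose effect, the mean test beats the high-dose test only when (1 + f)/2 > √((1 + r)/2), that is f > 2√((1 + r)/2) − 1. This gives 0.41, 0.58 and 0.73 for r = 0, 0.25 and 0.5. With 0.35 SD at the low dose, 0.70 SD at the high dose and r = 0.5, the mean test has 47% power and the high-dose test 59%.

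**Unequal SDs.** If the high-dose SD is 1.5 times the low-dose SD, the SD of the mean relative to the low-dose SD is √(1 + 2.25 + 3r)/2. That is 0.90 at r = 0 (a 10% cut) and 1.09 at r = 0.5 (a 9% increase). Against the high-dose test the cut is 40% or 27%.

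**The case against.** Dose-by-dose evaluation is the plan's convention for the primary endpoint and for the secondary changes, so the genotype analysis is consistent with the rest. It is exploratory, carries no power claim and cannot alter the primary conclusion. Section 13.5 already commits to cautious interpretation. Both changes will be collected, so a pooled analysis could be run later. All of this stands, and it limits the point to a refinement. It does not supply an overall test or a rule for discordant results, and a pooled test chosen after seeing the per-dose results would be less credible than a prespecified one.

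A reader might infer that the plan makes a real genotype modifier more likely to be missed. That does not follow. It is true against a single-dose test, but the plan runs two unadjusted tests per gene. The chance of at least one hit is lower than for the mean test only near r = 0; it is about equal at r = 0.25 and higher above that. The price is the per-gene false-positive rate of about 9-10% at r between 0.5 and 0.

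A reader might also infer that the mean-change test should replace the per-dose tests. The documents do not support that either. Dose-response is itself a secondary objective, and a genotype effect in the same direction but much larger at one dose is enough to make the overall test weaker than that dose's own test.

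**Conclusion.** The point holds as a gap in an exploratory analysis: four dose-specific tests, no overall test per gene, and an objective that names no dose. Under an identical 0.70 SD effect at both doses with a 20/21 split, roughly a third to a half of trials (33-48% for r = 0.5 to 0) would be significant at one dose only.

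The 13-29% reduction in detectable difference is conditional on r between 0.5 and 0, equal SDs, and a similar genotype effect at both doses. None of these is given in the documents, so it should not be read as a fixed property of the design. With equal SDs and a common effect, the direction holds for any r below 1 and any split, but the gain may be small. What the added test secures is one answer per gene at a 5% error rate. This is a low-cost improvement that would be good to have; it is not a flaw in the trial's main inference.

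**What to change.** In section 13.5, add one overall test for each gene and name it as the main genotype result. Preferably this is a genotype term in a linear mixed model of both benzene changes, with dose, period and a participant random effect, extending the model type already planned for dose-response. It can also use participants who have only one change. The simpler alternative is a two-sample t test on each completer's mean change over the two periods.

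Keep the four per-dose comparisons as supportive results, with estimates and confidence intervals. Report a genotype-by-dose term from a separate fit as a check, so that significance at one dose alone is not taken as evidence that the effect differs by dose.

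The cost is a few sentences of SAP text, with no new data, visits or participants. The downside is lower power than the better dose's own test if the genotype effect is concentrated at one dose, which is why the per-dose results should stay.

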7. CLINICAL EVALUATIONS AND PROCEDURES

7.1 Schedule of Events

	Pr				Stud	ly Intervention	n ¹			
	Interv	ention		vention Perio (10-14 days)			Inter	vention Per (10-14 days		
Procedure/ Evaluation	Visit 1 Screening	Randomization	Visit 2 Baseline	Visit 3 Intervention Period Day 4,5,6,7 or 8	Visit 4 End of Intervention	Washout Period ³ (10-14 days)	Visit 5 Baseline	Visit 6 Intervention Period Day 4,5,6,7 or 8	Visit 7 End of Intervention	Follow-Up ¹⁰
Informed consent	X									
Eligibility assessment	х									
Medical history	Х									
Concomitant medications	Х	Х	Х	Х	Х	Х	Х	Х	Х	
Blood for CBC-diff, CMP4	Х								Х	
Vitals (height, weight, temp, BP, heart rate) ⁵	х		х		x		х		х	
Brief physical exam	Х									
Karnofsky performance status	Х									
Tobacco Baseline Assessment Questionnaire	х									
Tobacco Follow up Assessment Questionnaire									х	
Alcohol Baseline Assessment Questionnaire	х									
Alcohol Follow up Assessment Questionnaire									х	
Query current tobacco use ¹¹	Х		Х	Х	Х		Х	Х	Х	
Urine pregnancy test ⁶	Х		Х				Х			
Overnight urine ⁷			Х		Х		Х		Х	
Buccal cell collection			Х	Х	Х		Х	Х	Х	
Nasal brushing collection			Х		Х		Х		Х	
Research blood collection			Х		Х		Х		Х	
Dispense Study Agent ⁸			Х				Х			
Collect Study Agent					Х				Х	
Review Agent Diary/Record				X	Х			Х	Х	
AEs		Х	Х	X	Х	Х	Х	Х	Х	X
Telephone/email Contact9		Х	Х	Х	Х	Х	Х	Х	х	Х

¹Study intervention to initiate within 30 days of screening unless significant scheduling problems arise.

² Intervention Period Day 1 is defined as the first day the dose is taken; each Intervention period is to last 10-14 days. For scheduling problems, agent intervention can continue beyond 14 days but no more than 21 days.

³Washout period for 10-14 days. For scheduling problems, the washout period can continue beyond 14 days but no more than 28 days.

⁴ CMP includes serum glucose, urea nitrogen, creatinine, sodium, potassium, chloride, bicarbonate, total protein, albumin, calcium, alkaline phosphatase, ALT, AST, total bilirubin. Calculations included with the CMP are: BUN/creatinine ratio, anion, gap, globulin, alb/glob ratio.

⁵Height required at Visit 1 only.

⁶For women of childbearing potential.

⁷ Overnight urine to be collected the night prior to the visit. If urine collection was missed the night prior to the visit, overnight urine may be collected the night of the visit.

⁸ Avmacol® pills may not be dispensed before confirmation of overnight urine collection.

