8. CRITERIA FOR EVALUATION AND ENDPOINT DEFINITION

8.1 Primary Endpoint

The primary endpoint is to determine the change (from baseline to end-of-intervention for each Intervention Period) in the urinary excretion of the mercapturic acid of benzene after Avmacol® intervention. The urinary levels of mercapturic acid of benzene will be normalized by urinary creatinine levels to account for varying water content of individual urine samples. The normalized mercapturic acid of benzene at end-of-intervention will be compared with that at baseline. The changes following 4 tablets of Avmacol® per day and after 8 tablets of Avmacol® per day will be determined separately.

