13.4 Primary Objective, Endpoint(s), Analysis Plan

The primary objective of this study is to determine whether Avmacol® increases the urinary excretion of the mercapturic acid of the tobacco carcinogen, benzene, in healthy current smokers. The primary endpoint is the change (from baseline to end-of-intervention for each Intervention Period) in the mercapturic acid of benzene after Avmacol® intervention. The changes following 4 tablets of Avmacol® per day and after 8 tablets of Avmacol® per day will be determined separately. Two-sided paired t tests will be performed to evaluate whether the changes are significantly. Bonferroni correction will be used to correct for multiple comparisons (two dose levels). With a sample size of 41 and an overall significance level of 5% (based on Bonferroni correction, i.e. a 2.5% significance level for each test), there will be at least 80% power to detect an effect size of 0.50 standard deviations. This is in line with an effect size of 0.45 standard deviations for a similar study (49).

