13.8 Evaluation of Response

All subjects with endpoint data will be assessed for response to intervention, based on the endpoints described above in Sections 13.4 and 13.5.

Sub-analyses may be performed on the subsets of participants, excluding those for whom major protocol deviations have been identified (e.g., early discontinuation of intervention, major protocol violations, etc.). However, sub-analyses may not serve as the basis for drawing conclusions concerning efficacy, and the reasons for excluding participants from the analysis should be clearly reported.

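### If more than 15% of the primary changes are missing, is it unclear whether the imputed or the observed-pairs result decides the test?

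*Combined protocol and SAP*

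**What the plan says.** Section 13.4 sets the primary test, one per dose: "Two-sided paired t tests will be performed to evaluate whether the changes are significantly". Each is run at "a 2.5% significance level for each test", and power is computed for 41 participants. Section 8.1 defines the comparison: "The normalized mercapturic acid of benzene at end-of-intervention will be compared with that at baseline".

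Section 13.3 starts 61 participants on agent and arrives at 41: "With an anticipated attrition rate of 33% or less". There, attrition covers both failing to finish the intervention and lacking complete endpoint data.

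The missing-data rule closes Section 13.5 and applies to every endpoint: "if a missing rate of >15% is observed, multiple imputation by chained equations will be performed". The same paragraph adds: "Regression techniques will be used to control for baseline levels and potential confounders if necessary".

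Section 13.8 describes who is analysed: "All subjects with endpoint data will be assessed for response to intervention". It ties that assessment to the endpoints of Sections 13.4 and 13.5.

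Note 8 to the schedule in Section 7.1 bears on what data will exist: Avmacol "pills may not be dispensed before confirmation of overnight urine collection".

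**The concern.** The planned attrition ceiling is about twice the imputation trigger, so the trial could produce two versions of each primary test: one on observed pairs and one on imputed data. The power statement, the count of evaluable participants and the first sentence of Section 13.8 all point towards observed pairs. The rule in Section 13.5 points towards imputation. Nothing states which one carries the conclusion, and nothing lists the variables in the imputation model.

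This could matter because the endpoint is a change from baseline. If smokers with high baseline values are lost more often, those who remain start lower, and regression to the mean pushes their average change upwards. If smokers with low baselines are lost, the average is pushed downwards. Imputation that uses the period's baseline corrects this, whereas imputing the change alone does not. At stake would be a false claim of increased excretion, a missed real increase, or a choice between two results once both are known.

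**Working it through.** **Step 1: the plan's own power.** Inputs from Section 13.4: n = 41, effect 0.50 SD of change, two-sided level 0.025. The noncentrality is 0.50 × √41 = 3.20 and the critical t on 40 df is 2.329. Exact noncentral-t power is 80.5%. With n = 40 it is 79.3%, so 41 is the smallest n that reaches 80%. Accrual: 61 × 0.67 = 40.9. The stated figures reproduce.

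**Step 2: when the rule applies.** 0.15 × 61 = 9.15, so 10 missing changes for a dose are needed (9/61 = 14.8%, 10/61 = 16.4%). The planned ceiling is 20/61 = 32.8%. The binomial chance of 10 or more missing for a given dose depends on when people leave. If all losses fall in Period 2, only the 30 or 31 people taking that dose second can be missing.

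| Attrition | All lost before Visit 4 (n = 61) | All lost in Period 2 (n = 30 / 31) |
|---|---|---|
| 33% | 99.9% | 55% / 60% |
| 25% | 96% | 20% / 23% |
| 20% | 80% | 6% / 7% |
| 15% | 43% | 1% / 1% |

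**Step 3: random loss.** Simulation of one dose: 61 participants, 33% missing, normal data, assumed pre-post correlation 0.5, 40 imputations from a regression containing baseline, Rubin pooling, level 0.025, 2,000 trials per setting.

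| | Observed pairs | Imputed |
|---|---|---|
| Rejection at true change 0 | 3.0% | 2.7% |
| Power at 0.50 SD | 79.5% | 81.5% |

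Both are valid, with Monte Carlo error of about 0.35 and 0.9 percentage points. The verdicts still differ in 7.1% of trials at 0.50 SD. Two valid analyses of overlapping data will do that near the threshold.

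**Step 4: loss related to baseline (assumed).** Same setting, with log-odds of loss changing by 1 per baseline SD (odds multiplied or divided by about 2.7).

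| | Bias, observed pairs (SD of change) | Bias, imputed | Error at 0, observed / imputed | Power, observed / imputed |
|---|---|---|---|---|
| High baselines lost | about +0.14 | about 0 | 8.8% / 2.1% | 96% / 78% |
| Low baselines lost | about −0.14 | about 0 | 9.0% / 2.1% | 52% / 79% |

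A milder link was run in the full two-period design: 33% attrition, correlations 0.5 and 0.7, losses placed early, split or late, and imputation only for doses that trigger. If the odds of loss double per SD, observed pairs shift by 0.03-0.06 SD. Two-sided family-wise error is then 5.3-6.9% for observed pairs and 3.2-5.0% with imputation. If the odds halve, power per dose at 0.50 SD is 70-84% against 76-87%.

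**Step 5: where the contrast disappears.** If the change is independent of baseline, baseline-related loss biases neither analysis (both within 0.002 SD). Imputation only costs precision: power is 73% against 81%. If loss depends on the unseen change itself, both are biased by about 0.19-0.29 SD and imputation does not repair it.

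**Step 6: reading the sections together.** The rule in Section 13.5 is conditional and mandatory and names no exception for the primary endpoint. Section 13.8 sends the reader back to Sections 13.4 and 13.5, so it takes in the imputation rule rather than competing with it. Chained equations regress each incomplete variable on the others. Applied to the urine values at the four visits, they use a period's baseline as a matter of course, and note 8 to Section 7.1 means that anyone who starts a period has that baseline.

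**The case for a change.** The case for a change is that the gap is real, likely to arise and cheap to close. No sentence ranks the two results. Section 13.4 powers the test on observed pairs, so a reader could fairly take imputation as supplementary. The baseline regression in Section 13.5 is optional and not linked to missing data. Even with random loss, the full-design simulation gives different verdicts for at least one dose in 7-14% of trials at 0.50 SD. With doubled odds of loss, observed pairs falsely claim an increase in 4.3-6.2% of trials against 1.4-3.0% with imputation (nominal about 2.5%). Imputing the change without its baseline keeps most of the error, at 3.0-5.4%.

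The omission, the trigger arithmetic and the direction of the bias all stand. The size does not stand as a property of this trial, because the loss strengths and correlations are assumed and nothing in the documents ties loss to baseline excretion. The missing rate may also fall short of the attrition rate. Section 8.3 keeps collecting endpoint data after agent is stopped, Section 5.6 encourages early withdrawals to return for samples, and a Period 2 dropout still supplies the Period 1 change.

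One point limits imputation as well. Someone lost before Visit 4 normally has no Visit 5 urine, so the second dose's own baseline is missing and only earlier values can inform it.

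**Conclusion.** No change to the plan follows. The text leaves a detail unstated that analysts fill sensibly: above 15% missing, the required imputation is the analysis, the observed-pairs test is reported beside it, and the imputation model carries the urine values including each period's baseline. On that reading there is no free choice between two primary results.

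The test, the Bonferroni split and the 80.5% power at n = 41 are sound. With random loss the two analyses are equally trustworthy. A difference in reliability needs loss tied to baseline together with a change correlated with baseline. Under an assumed doubling of the odds of loss, two-sided family-wise error for observed pairs reaches 5.3-6.9% against 5%, a modest excess; it grows only under stronger assumed links. If loss depended on the unseen change, naming the deciding analysis would not help. All simulated sizes assume normal data, whereas Section 13.5 already provides for transformation or a signed-rank test.
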